The trial will involve 6 CADCs across the sites; 3 CADCs (2 from OSLC and 1 from CLA) will be randomly selected to deliver CM+ and the other 3 CADCs (2 from OSLC and 1 from CLA) will deliver standard family-based CM. Based on our experience with RCTs, we anticipate turnover and have planned for as-needed recruitment of new CADCs and case re-assignment to ensure cases remain within condition. To ensure high fidelity and reduce confounding variables (e.g., access, insurance), the study will pay for treatment in both conditions, and investigators will train and closely monitor CADC staff.

Adolescents presenting to OSLC and CLA for SUD treatment during Study Months 7-42 will be screened, and those meeting inclusion criteria will be offered the opportunity to participate pending available slots. Power calculations (presented subsequently) indicate an optimal sample size of 172. Given case flow at the clinics, and our desire to oversample Latino families, we anticipate achieving the required sample size in 3 years. Specifically, CLA treats 23 adolescents with SUD per year on average, and all of these will be approached to participate in

the trial. Assuming an 80% recruitment rate (see subsequent rationale for this rate), we expect to recruit 55 families from CLA across the 3 years. OSLC serves just over 100 cases/year on average, so case flow will provide more than enough families to recruit the remainder of the sample (49/year x 3 years = 117). Based on information from OSLC and CLA, the following demographic characteristics are expected for youth recruited across both clinics: average age = 15 years (range = 12-17 years); 84% White, 13% African American, 2% American Indian/Alaska Native, 1% Asian; 35% Latino (of any race); and 30% female.

PARTICIPANTS

Participants will include 172 youth and their primary parent/guardian. Inclusion criteria for the youth are: 1) age 12-17 years; 2) presence of current SUD; and 3) availability of a parent/guardian willing to participate. Exclusion criteria are: 1) actively psychotic, suicidal, or homicidal; and 2) PDD or mental retardation. To increase external validity, youth will be included regardless of co-morbid mental health or physical difficulties.

RESEARCH SCREENING, RECRUITMENT, AND RETENTION

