EXPERIMENTAL MEDIATION AND CAUSAL INFERENCE. The experimental mediation design emphasizes evidence supporting causal inferences, and there are important conceptual and statistical considerations. As reviewed by [name], ¹⁹⁹ by randomizing youth/parents, the effect of CM+ on parent management is a causal estimate. However, the effect of parent management on drug use and externalizing behavior is not straightforwardly causal, it is potentially influenced by unmeasured confounding variables. Following [name]'s

recommendations, and to support causal inferences, this is addressed in 3 ways. First, the enhancement design directly targets the mediator—increasing probability of a causal effect between mediator and outcome. Second, longitudinal measurements of the mediator and outcomes address temporal sequencing—demonstrating that mediator effects occur before outcome effects. Third, supplemental models evaluate confounding variables—providing evidence that mediator effects are not due to confounders.

MODEL FORMULATION. The underlying model is a mixed-effects latent growth curve model with repeated measurements (level-1) nested within youth/parents (level-2), implemented in Mplus (v7.31;¹⁹⁷). As reviewed by [name],²⁰⁰ there are several options for modeling longitudinal mediation. Flexibility of growth models for targeting phase-specific change²⁰¹ are leveraged and combined with parallel process models for mediation.²⁰² In a single model, there are separate change estimates for during- and post-treatment phases, directly addressing temporal sequencing of mediators and outcomes. The UDS outcome is modeled using a Bernoulli distribution, and remaining ultimate outcomes, direct targets, and indirect targets are modeled with normal distributions. Time terms are computed using assessment dates.²⁰³ Treatment condition is a youth/parent-level predictor (level-2; CM = 0, CM+ = 1), and cross-level interactions are specified between condition and level-1 growth and phase terms. Models, as indicated, control for age, sex, race, ethnicity, SES, and treatment history. Likewise, preliminary models test, and control, for differences in outcomes across therapists and clinics. Follow-up models determine whether individual paths and mediated effects differ for males and females.

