STATISTICAL POWER FOR MEDIATED EFFECTS. The proposed mediation models include estimates of: (1) the effect of the initial variable on the hypothesized mediator (α-path), (2) the effect of the hypothesized mediator on the outcome (β-path), and (3) the mediated effect (αβ). Using Monte Carlo simulations implemented in Mplus, $^{214-215}$ power is determined by the percentage of replications with a significant effect for the path of interest. Using covariance algebra provided by Thoemmes et al., 215 parameters (path coefficients, variances, residuals) were tailored to reflect α- and β-paths with small-to-medium ($R^2 = .07$) effects. For each model, sample size, conservatively assuming 10% attrition, was 155, with 10000 replications from the population. For a-path, power was >.90 to detect a small-to-medium effect of the initial variable on the mediator. For β-path, power was .85 to detect a small-to-medium effect of intermediate targets on ultimate outcomes. For the mediated effect, power was .83. This estimate is conservative due to the simulation's Sobell *SE* method. As an upper bound on power, and based on simulations using the proposed asymmetric *SE* method, Fritz and MacKinnon²¹⁶ found a sample of *N*=74 sufficient for .80 power to detect medium effects for α- and β-paths.

ATTRITION AND MISSING DATA

Participants will be retained in research measurement independent of CM/CM+ participation following intent-to-treat principles.²¹⁷ Along with this, the successful participant tracking and retention protocols used in OSLC research will minimize missing data. However, because some data will inevitably be missing, methods recommended by Schafer and Graham²¹⁸ will evaluate assumptions and guide analyses. Three steps will be used: (1) For a small proportion of missing data with evidence of Missing at Random (MAR), data will be analyzed using the estimation procedures described above. (2) For a non-trivial amount of missing data and evidence of MAR, multiple imputation for repeated measurements will generate complete data.²¹⁹ (3) For a non-random missing data mechanism, pattern mixture models will identify and control its effects.^{203–204}

BIBLIOGRAPHY & REFERENCES CITED

- 1. [name], P., & Reid J. (1987). Parent observation and report of child symptoms. *Behavioral Assessment*, 9, 97-109.

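### One b-path power (.85) and one mediation power (.83) are given for all ultimate outcomes; if they come from a continuous-outcome simulation, they are too high for the binary urine drug screen

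*Combined protocol and SAP*

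**What the plan says.** Statistical Power for Mediated Effects reports a Monte Carlo simulation in Mplus. Its inputs are described only by kind: "parameters (path coefficients, variances, residuals) were tailored to reflect" paths with "small-to-medium ($R^2 = .07$) effects". The sample size, "conservatively assuming 10% attrition, was 155, with 10000 replications from the population", follows from 172 randomised.

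Three results are given:
- a-path: "power was >.90 to detect a small-to-medium effect of the initial variable on the mediator"
- b-path: "power was .85 to detect a small-to-medium effect of intermediate targets on ultimate outcomes"
- mediated effect: "For the mediated effect, power was .83"

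The section calls the last figure conservative because the simulation used Sobel standard errors.

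Data Analysis Strategy counts substance use and externalizing behavior as the ultimate outcomes and classes UDS as discrete. Model Formulation adds: "The UDS outcome is modeled using a Bernoulli distribution". The remaining ultimate outcomes, including the GAIN scores, are modelled as normal. Under Aim 1, the b-path regresses the 9- and 12-month outcomes on the during-treatment mediator slope.

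No section gives a UDS positive rate, threshold, odds ratio, within-youth correlation or separate power figure.

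**The concern.** One figure cannot hold for both a continuous and a binary outcome at the same underlying effect, because reducing a continuous trait to positive or negative discards information. If .85 belongs to the continuous outcomes, it is too high for UDS. If it belongs to UDS, the section omits the input that largely determines it, the positive rate.

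UDS is the only laboratory measure of substance use in Table 2; the GAIN scales are self-reported. Substance use is an outcome in Aims 1 and 3. A reader faced with a null mediated effect on UDS would turn to the power section and find .83, with nothing to say that it may not apply to this outcome.

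**Working it through.** **Inputs from the plan.** 172 randomised, 155 analysed (172 × 0.9 = 154.8); R² = .07 per path; stated powers >.90, .85 and .83. Two-sided 5% is assumed from the planned 95% intervals.

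**Assumed inputs (not in the documents).** UDS positive rate of 10% to 70%; latent within-youth correlation (ICC) of .3 to .7 between months 9 and 12; R² = .07 on the latent scale behind the binary result.

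**1. The plan's own figures.** In a single-level normal model with N = 155:
- a-path: noncentrality √(155 × .07/.93) = 3.42, power .92. This agrees with >.90.
- b-path: .905 to .936, depending on how R² = .07 is read. The stated .85 would need a partial R² of about .055.
- Mediated effect: .69 with Sobel standard errors; .84 if both paths must be significant. The stated figure is .83.

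So .85 and the Sobel .83 do not reproduce in this simple model. The growth-model inputs are not reported, so this does not show the simulation to be wrong. I therefore take .85 as given and ask what it implies for UDS.

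**2. Closed form, one occasion.** Power .85 corresponds to z = 1.96 + 1.036 = 2.996. The efficiency of a binary relative to a normal outcome is E = φ(z_p)²/[p(1−p)], and UDS power is Φ(2.996√E − 1.96).

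| Positive | E | 2.996√E | b-path power |
|---|---|---|---|
| 50% | .64 | 2.39 | .67 |
| 30% | .58 | 2.27 | .62 |
| 20% | .49 | 2.10 | .55 |

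**3. Closed form, months 9 and 12 pooled, 50% positive.** With latent correlation ρ, the binary results correlate at ρ_b = (2/π)·arcsin ρ, and E becomes .637 × (1+ρ)/(1+ρ_b). For ρ = .3, .5 and .7, ρ_b is .19, .33 and .49, E is .69, .72 and .72, and power is .70, .72 and .72. Pooling helps, but does not reach .80.

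**4. Logistic simulation** (N = 155, adjusted for treatment, 4,000 replicates per cell, Monte Carlo standard error at most .008). R² = .07 is set either on each occasion's latent value or on the person-level intercept. Anchored power multiplies 2.996 by the binary-to-normal ratio of z. Entries are for 10/20/30/50/70% positive.

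| Setting | Normal-outcome power | UDS power, direct | UDS power, anchored to .85 |
|---|---|---|---|
| One occasion | .91 | .39/.63/.75/.80/.76 | .33/.55/.67/.73/.68 |
| Two, occasion-level, ICC .3 | .98 | .69/.84/.91/.94/.90 | .43/.59/.67/.73/.66 |
| Two, occasion-level, ICC .5 | .97 | .66/.80/.85/.89/.86 | .46/.59/.66/.71/.67 |
| Two, occasion-level, ICC .7 | .95 | .62/.75/.82/.85/.81 | .48/.59/.67/.71/.66 |
| Two, person-level, ICC .3 | .61 | .29/.39/.45/.47/.44 | .47/.61/.69/.72/.68 |
| Two, person-level, ICC .5 | .77 | .40/.51/.58/.63/.58 | .48/.60/.67/.72/.67 |
| Two, person-level, ICC .7 | .85 | .49/.61/.66/.69/.66 | .49/.61/.66/.69/.66 |

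The ratio of z runs from .51 to .85. Keeping .80 from a start of .85 would need 2.80/2.996 = .935, which no setting reaches. The last row needs no anchoring: its normal-outcome power is already .85.

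**5. Mediated effect.** Requiring both paths to be significant, with a-path z = 3.42 (power .93), gives .31 to .67 for UDS. The same rule applied to the plan's b-path gives .85 × .93 = .79, so .79 is the like-for-like comparator. Scaling by the plan's own ratio instead gives .33 × .83/.85 = .32 to .73 × .83/.85 = .71, to be set against .83.

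**The case against.** The strongest reply is that the plan never names the simulated distribution. A Bernoulli outcome has no free residual variance at the measurement level, but in a mixed-effects growth model it can still carry person-level variances and residuals, and the b-path predictor is a person-level slope. The text also refers to more than one simulated model. This stands: a continuous outcome is an inference, though a well-supported one, since a binary simulation needs a base rate or threshold and none is mentioned.

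A second reply is that UDS power may be adequate. Taken directly from N = 155 and R² = .07, two occasions with occasion-level R² give .80 to .94 in most cells at 30% to 70% positive. But the matching continuous-outcome power there is .95 to .98, which is not the plan's .85. That reading rescues UDS only by giving up the stated figure.

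A reader might go further and infer that UDS power is simply well below .80. The documents do not support this unconditionally: the positive rate, the correlation and the scale of R² are all unstated, and direct values run from .29 to .94.

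A reader might also subtract product-rule mediation powers from .83. That is not like-for-like, because the same rule gives about .79 for the plan's own b-path.

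Finally, substance use is also measured by continuous GAIN scales, to which the figures can still apply, and the plan reports confidence intervals for the product. Nothing in it says that a null UDS result would be read as evidence against the mechanism.

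**Conclusion.** The concern holds in conditional form. The power statement covers all ultimate outcomes with one figure, UDS is binary, and no UDS power is reported. If .85 is the continuous-outcome figure and the latent effect is the same, b-path power for UDS is about .55 to .73 at 20% to 70% positive and about .33 to .49 at 10%. Mediated-effect power is about .31 to .67 under the joint test. These ranges rest on assumed positive rates, on correlations of .3 to .7 and on a latent-scale R².

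The direction does not depend on those choices: the binary outcome lost power in every setting examined. The documents do not show that the .85 or .83 was miscalculated for continuous outcomes, and the point gives no ground for ranking GAIN above UDS.

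**What to change.** In Statistical Power for Mediated Effects:
- State the outcome distribution and the parameter values used in the simulation.
- If the outcome was continuous, limit .85 and .83 to the GAIN scales and externalizing behavior.
- Rerun the existing Monte Carlo with a categorical UDS at 9 and 12 months, over a stated range of positive rates and within-youth correlations, and report the resulting b-path and mediated-effect power for UDS.

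The sample size, visits and outcome hierarchy stay as they are. The cost is a small rerun of existing code and a less favourable stated figure for UDS.

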STATISTICAL TEST FOR MEDIATION. The test for mediation is based on the product of coefficients (i.e., $\alpha\beta$) with asymmetric bootstrapped *SE*s and 95% CIs for the product.²⁰⁴ This test requires estimation of two parameters and their *SE*s, where, for example, α is the effect of CM+ on parent management and β is the effect of parent management on substance use and externalizing behavior. Parameters are obtained from Mplus and supplied to PRODCLIN²⁰⁵ for the asymmetric boostrapped *SE*s and CIs. This approach offers enhanced statistical power²⁰⁶ and applies both to multilevel data²⁰⁷ and longitudinal mediation.²⁰⁰

EVALUATION OF SPECIFIC AIMS

AIM 1: DETERMINE WHETHER PARENT MANAGEMENT SKILLS (DIRECT TARGET) MEDIATE THE EFFECT OF TREATMENT ON YOUTH SUBSTANCE USE & BEHAVIOR PROBLEMS (ULTIMATE OUTCOMES). The test for mediation requires the coefficient and SE for CM+'s effect on parenting (a-path) and parent management's effect (controlling for treatment) on substance use and externalizing behavior (b-path). Of note, a preliminary model evaluates the direct effect of CM+ on substance use and externalizing behavior (c-path), though as noted by [name], ¹⁹⁹ mediation should be tested regardless of this path's significance.

a-path. This model is specified with 11 repeated measurements of parenting as the outcome. To address temporal sequencing, the model estimates separate change rates for during- and post-treatment phases. This is tailored to each youth's course of treatment using coding strategies for discontinuous (piecewise) change (see Singer and Willett²⁰¹). Changes during treatment phase are modeled with linear and quadratic terms for number of months since baseline. A dichotomous phase indicator differentiates post- and during-treatment measurements, and post-treatment change is modeled as linear and quadratic terms for number of months since treatment end. This provides three estimates: during-treatment slope (estimate of interest for mediation test), overall shift in parenting levels from during- to post-treatment, and post-treatment slope.

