AIM 2: DETERMINE WHETHER PARENT MANAGEMENT SKILLS (DIRECT TARGET) MEDIATE THE EFFECT OF TREATMENT ON YOUTH BEHAVIORAL REGULATION & DEVIANT PEER RELATIONS (INDIRECT TARGETS). In the parallel process model for Aim 2, the *a-path* is identical to that for Aim 1. The "outcome" model is nearly identical, the only difference being that the "outcomes" are indirect targets of treatment, behavioral regulation and peer relations. The b-path coefficient represents the association between the during-treatment slope for parent management and the 9- and 12-months post-treatment levels of behavioral regulation and peer relations.

AIM 3: DETERMINE WHETHER BEHAVIORAL REGULATION & DEVIANT PEER RELATIONS (INDIRECT TARGETS) MEDIATE THE EFFECT OF PARENT MANAGEMENT SKILLS (DIRECT TARGET) ON YOUTH SUBSTANCE USE & BEHAVIOR PROBLEMS (ULTIMATE OUTCOMES). Aim 3 uses the same approach, with one key difference: rather than treatment condition, the initial variable is parent management (the direct target of treatment) and, as such, there are repeated measurements. The *a-path* represents the effect of parent management on behavioral regulation and deviant peer relations. With both measured longitudinally, this takes the form of the during-treatment slope for parent management predicting the during-treatment slope for behavioral regulation and deviant peer relations. Although this could confound timing and sequencing of a-path effects, the results of Aim 2 will have established the extent to which there is evidence supporting a causal association between the direct and indirect targets of treatment. The outcome model is identical to that for Aim 1. The *b-path*, holding constant the effect of parent management, is the effect of the during-treatment slopes for behavioral regulation and peer relations on the post-treatment levels of substance use and behavior problems.

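### The stated mediated-effect power of .83 with a Sobel standard error does not follow from the stated inputs (R² = .07 on both paths, N = 155), so the reserve implied by calling it conservative is unsupported

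*Combined protocol and SAP*

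**What the plan says.** Under Statistical Power for Mediated Effects, the simulation's path coefficients, variances and residuals were set to represent "small-to-medium ($R^2 = .07$) effects" on both paths. On sample size: "For each model, sample size, conservatively assuming 10% attrition, was 155". The section then reports three results:

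- a-path: power above .90, with no upper limit given;
- b-path: "power was .85 to detect a small-to-medium effect of intermediate targets on ultimate outcomes";
- product of the two paths: "For the mediated effect, power was .83. This estimate is conservative", attributed to the Sobel standard error used in the simulation.

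The planned test is a different one. Statistical Test for Mediation specifies a 95% asymmetric interval for the product of coefficients: "Parameters are obtained from Mplus and supplied to PRODCLIN". The Study Sites section makes power the basis for enrolment, saying that the calculations "indicate an optimal sample size of 172". The parameter values, the direct effect, the significance level of the simulation and the variance to which R² refers are not reported.

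**The concern.** The Sobel test is usually less powerful than an asymmetric product interval. A reader told that .83 is a Sobel figure will therefore conclude that the planned test does better than .83 at R² = .07.

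The three reported powers are hard to reconcile with that. The Sobel statistic is always smaller in absolute value than either path's own z statistic. With a b-path power of .85, a Sobel power of .83 leaves only two points to lose to the a-path, so the a-path would have to be detected almost without fail. An R² of .07 in 155 families does not give that.

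At stake is the support for 172. If the planned interval's power is not above .83 but somewhere between the high .70s and the mid .80s, the plan should say so. At present it gives no computed figure for its planned test at its own effect size.

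**Working it through.** **Inputs from the documents.** Randomised 172; analysed 172 × 0.90 = 154.8, taken as 155. R² = .07 on each path. Stated powers above .90, .85 and .83.

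**Assumptions.** Two-sided .05, matching the planned 95% interval; one mediator; 1:1 allocation; uncorrelated path estimates.

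**Step 1: a-path.** f² = .07/.93 = .0753. Expected z = √(155 × .0753) = 3.416. Power = Φ(3.416 − 1.960) = .927. This agrees with the stated value above .90.

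**Step 2: b-path.** If R² is partial (initial variable held constant), expected z is again 3.416 and power .927. If R² is zero-order with no direct effect, expected z = √(155 × .07) = 3.294 and power .909. The stated .85 corresponds to z = 1.960 + 1.036 = 2.996, which neither reading gives.

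**Step 3: product.** Sobel z = z_a·z_b / √(z_a² + z_b²). The product interval excludes zero when Φ(−z_a)Φ(z_b) + Φ(z_a)Φ(−z_b) is below .025 or above .975. Power is the share of simulated (z_a, z_b) pairs, or of simulated regressions, that pass.

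| N = 155, R² = .07 on both paths | a | b | Sobel | Product interval |
|---|---|---|---|---|
| Normal theory, partial R² | .93 | .93 | .72 | .85 |
| Normal theory, zero-order R² on b | .93 | .91 | .69 | .83 |
| Regression simulation, partial R² | .923 | .917 | .708 | .841 |
| Regression simulation, zero-order R² on b | .924 | .898 | .680 | .823 |

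A standardised direct effect of .265 raises Sobel only to .72–.74 and the product interval to .85–.86. Across all variants Sobel is .68–.74 and the product interval .82–.86. With no attrition (N = 172), Sobel is .76–.81. For Sobel to reach .83 at R² = .07 would take about 182 to 192 analysed, or at N = 155 an R² of about .081 to .086 on both paths.

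**Step 4: start from the stated b-path power.** Hold the b-path at .85 (z = 2.996) and vary the a-path:

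| a-path z | a-path power | Sobel | Product interval |
|---|---|---|---|
| 3.416 (R² = .07) | .93 | .61 | .78 |
| 4 | .98 | .71 | .83 |
| 5 | .999 | .79 | .85 |
| 6 | >.999 | .82 | .85 |
| 7 | >.999 | .83 | .85 |

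Converting z = 7 back: f² = 49/155 = .316, so R² = .316/1.316 = .24. At z = 7.2, R² = .25. The three stated figures therefore fit a Sobel standard error only with a person-level a-path R² of about .25.

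**Step 5: the Aim 3 model.** The b-path sentence refers to intermediate targets, which fits Aim 3, where the b-path is estimated "holding constant the effect of parent management". With two correlated mediators (correlation assumed, .2 to .5; none is given) and R² = .07 on the a-path and the tested b-path, b-path power can fall to .85 (at r = .4, second mediator without effect). Sobel is then .618 and the product interval .775. Over all the cases run, Sobel is .57–.71; none reaches .83.

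**The case against.** The strongest reply is that a cross-sectional single-mediator regression is not the planned model. The plan uses parallel-process growth models with 11 mediator and 6 outcome measurements, and its simulation parameters are not reported. The standard model also misses the stated .85, so the sponsor's simulation probably had another structure. This stands, and it limits the point to non-reproduction.

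Second, the three powers can coexist with a Sobel standard error, because above .90 has no ceiling. If .07 referred to repeated observations (assumed intraclass correlation .15 to .30), 155 × 11 = 1,705 observations would have an effective size of 1,705/2.5 = 682 to 1,705/4 = 426, and an a-path z of 7.2 to 5.7. Nothing in the documents says R² is defined that way. By the conversion in Step 4 it would also mean a person-level R² of about .25 to .17, which is no longer a small-to-medium effect of .07.

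Third, Sobel power is below product-interval power in every uncorrelated case here, so the direction of the plan's remark is right. That stands. What is not supported is the .83 from which the remark starts.

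One-sided .05 does not resolve it. Sobel becomes .84–.88, but the b-path rises to about .95–.96; set to .85 one-sided, Sobel is about .72. A one-sided test also does not match the planned 95% interval. A negative correlation between the path estimates of about −.23 (R² = .07 on both) or −.42 (b-path at .85) would give .83, but the plan reports no such correlation.

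A reader might infer that .83 is really the planned interval's power, mislabelled as Sobel. The match holds only where b-path power is about .90 or more; at the stated .85 the interval gives .78. A reader might also fault the cited N = 74 result, "sufficient for .80 power to detect medium effects". The plan presents it as an upper bound and names the larger effect, so there is no fault there.

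**Conclusion.** The concern holds as a failure to reproduce. At R² = .07 on both paths and N = 155, Sobel power is about .68 to .74 against the stated .83, a gap of 9 to 15 points. With the b-path at the stated .85 and the a-path at R² = .07, Sobel power is about .61, a gap of 22 points. In the same model the planned interval has about .78 (b-path at .85) to .82–.86 (R² = .07 on both), so a reserve above .83 is not supported.

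This rests on a standard single-mediator model, two-sided .05 and uncorrelated path estimates. It would be overturned if the reported growth-model inputs gave .83 with a Sobel standard error at a person-level R² of .07.

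A reader might go further and conclude that the trial is underpowered. The documents do not support that: at R² = .07 on both paths the planned interval is above .80, and only the reading with the b-path at .85 falls slightly below. The point should be fixed because power is the stated ground for 172.

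**What to change.** Re-run the simulation at R² = .07 and N = 155. Replace the .83 and its conservative label with the power of the planned asymmetric product interval, and label any Sobel value as such. Reconcile the .85 b-path figure with R² = .07, stating which aim's model it comes from and which variance R² refers to. The re-run sets the number; none is proposed here.

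The cost is one simulation re-run and a possibly less favourable stated power. Enrolment and the planned analysis are unchanged.
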